8.3. Packaging and Labelling

From the documentation of the trial medication, it must be possible to retrace the handling, composition and pharmaceutical quality of the investigational products according to the current Good Manufacturing Practice (GMP) guidelines.

TG02 will be packed and labelled by [REDACTED], a specialised pharmaceutical clinical supply company located in [REDACTED], in accordance with GMP and International Conference on Harmonisation (ICH) Good Clinical Practice (GCP) requirements. The vials and boxes will be labelled according to local regulatory requirements.

The trial medication will be supplied to the investigational site(s) in boxes containing a defined number of vials. TG02 will be shipped to the investigational sites under controlled, frozen (-20±5 °C) conditions.

GM-CSF will be packed and labelled by [REDACTED], a specialised pharmaceutical clinical supply company located in [REDACTED] in accordance with GMP and International Conference on Harmonisation (ICH) Good Clinical Practice (GCP) requirements. The vials and boxes will be labelled according to local regulatory requirements.

The trial medication will be supplied to the investigational sites in boxes containing “a defined number of vials”. GM-CSF will be shipped to the investigational site(s) under controlled, refrigerated conditions (2 -8 °C).

Pembrolizumab, in the Part II of the study, will be supplied from commercial stock at the clinical site(s) or sourced, packed and labelled and supplied by [REDACTED], a specialised pharmaceutical clinical supply company located in [REDACTED] in accordance with GMP and International Conference on Harmonisation (ICH) Good Clinical Practice (GCP) requirements. The vials and boxes will be labelled according to local regulatory requirements.

The trial medication will be supplied to the investigational sites in boxes containing “a defined number of vials”. Pembrolizumab will be shipped to the investigational site(s) under controlled, refrigerated conditions (2 -8 °C).

8.4. Storage, Handling and Dispensing of Investigational Product(s)

Upon receipt of the medication, the Investigators, or the responsible pharmacist, will inspect the medication and send back the acknowledgment of receipt form that is enclosed with the parcel, duly completed and signed and further follow up on the instructions given in the shipment documents. A copy of the signed receipt will be kept in the trial files. TG02 must be kept frozen at -20 ± 5 °C and GM-CSF must be kept at 2-8 °C during storage prior to reconstitution. Pembrolizumab must be stored at 2-8 °C in original carton to protect from light. Do not freeze. Do not shake.

All study drugs are to be stored safely and separately from other drugs. The trial medication cannot be used for any purpose other than the present study. After the trial is completed, all unused trial medication must be destroyed by the pharmacy after sponsor’s approval.

The Investigators will be responsible for the storage, dispensing, inventory, and accountability of all clinical supplies at the clinical sites. An accurate, timely record of the disposition of all clinical supplies must be maintained. The supplies and inventory must be available for inspection by the designated representatives of the Sponsor (Targovax) on request, and must include the information below:

- the identification of the patient to whom the drug was dispensed
- the date(s) and quantity of the drug dispensed to the patient
- the product lot number

The preparation of the Study Drugs must be documented on a ‘Drug Preparation and Dispensing Log Form’.

A copy of the inventory record and a record of any clinical supplies that have been destroyed must be submitted by the Investigators to the Sponsor (Targovax). This form must include the information below:

- the number of administered units
- the number of unused units
- the number of units destroyed at the end of the trial
- the date and method of destruction and the location

8.5. Blinding Procedures

The study will be an open labelled study.

8.6. Randomization and Subject Allocation

This is a non-randomized study.

8.7. Treatment Compliance

The Investigator(s) will record the time and dose of all administrations in the medical source documents. Any reasons for non-compliance will also be documented, including:

- missed visits
- interruptions in the schedule of administration
- non-permitted medications

Management of Toxicity

If a patient experiences GM-CSF or TG02 related toxicity on the days of the scheduled TG02 treatment, TG02 treatment should be delayed until toxicity resolved to CTC grade 1. The patient should then restart at the next planned visit.

Management of TG02 or GM-CSF related reactions:

- At any time during the vaccination schedule – if a patient exhibits signs of an allergic reaction (not just a local reaction) then they should be treated symptomatically and for all subsequent TG02-treatment administrations they should be pre-medicated with intravenous antihistamine treatment (e.g. chlorpheniramine or dexchlorpheniramine) 30 minutes before any TG02-treatment administration.
- Patients who have local reactions only – It is permissible to use topical therapies such as anti-histamine or steroid creams or EMLA cream for pain
- Where a DTH injection is being performed the TG02 DTH dose should be administered **30 minutes** before the TG02-treatment and patients should be observed for at least 30 minutes after ALL TG02-treatments.
- In patients who have not had prophylaxis
 - If after the TG02 DTH dose the patient exhibits a Grade 1 or 2 allergic reaction then the TG02-treatment should be delayed and the patient is to be given intravenous antihistamine treatment as above
 - If a Grade 3 or 4 reaction occurs then no more vaccinations should be given.
- In patients who have had prophylaxis
 - If after the DTH dose the patient exhibits a Grade 1 reaction then the TG02-treatment should only be given if the investigator believes it is reasonable to do so based on the nature of the reaction
 - if a Grade ≥ 2 reaction occurs then no more vaccinations should be given.
- Precautions should be in place in case of anaphylaxis

Management of pembrolizumab related reactions:

- Toxicities should be managed according to SmPC for pembrolizumab. The patient should be discontinued if immunosuppressive agents are used at immunosuppressive doses. Please see *Section 8.8 Prior and Concomitant Medication* for further details.

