- 6: If surgery is scheduled after Day50/Week 8, pembrolizumab will be given at Day 50/Week 8. If surgery scheduled after Day 64/Week 10, a further pembrolizumab infusion will be given at Day 64/Week 10.

Part I

Approximately 4-6 patients diagnosed with locally advanced primary and recurrent colorectal cancer will be given TG02-treatment for up to 10 weeks (up to 6 TG02-treatments) prior to surgery.

TG02 is an eight peptide vaccine. Significant clinical data exists for its precursor vaccine, TG01, which contains 7 of the 8 mutant RAS peptides present in TG02. TG01 in combination with GM-CSF has been shown to be immunogenic and well tolerated up to 11 weeks of treatment.

Since one of the eight peptides in TG02 has not previously been administered to humans, the first 3 patients will be enrolled in a sequential manner with a minimum lag time of 4 weeks between dosing of the first 3 subjects to ensure an acceptable safety profile.

The safety data collected during the first 4 weeks for the three first patients will be reviewed by a SSC consisting of Sponsor representatives, the Principal Investigator, relevant Sub-Investigators and one Independent Physician.

As a general rule the following will be reviewed to provide a guide to safety decisions:

Unacceptable toxicities will be defined as follows (based on NCI Criteria for Adverse Events (CTCAE) (v4.03: June 14, 2010) for reactions considered related to TG02 and/or GM-CSF:

- Injection site reaction of \geq grade 3 (grade 3: Ulceration or necrosis; severe tissue damage; operative intervention indicated, grade 4: Life-threatening consequences; urgent intervention indicated, grade 5: death).
- Other relevant clinically significant toxicity \geq grade 3 (excluding treatable nausea and vomiting). However, for certain toxicities such as laboratory assessments without a clear clinical correlate, a discussion in the SSC may take place to evaluate if this AE should be assessed as DLT.
- \geq Grade 3 'allergic reaction/anaphylactic reaction' in spite of prophylaxis with antihistamine and steroids.

All AEs and SAEs will be reviewed and will also be compared to those of the precursor vaccine TG01 (see Investigator's Brochure).

If more than 1 out of the 3 patients has DLT the SSC will review the nature of the events and make a final decision if the rest of the patients may be enrolled.

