The treatment period will be from Day 1 (Week 1) and up to surgery, which is planned for week 8 but can occur in a window up to week 14. The following assessments will be performed on Day 1, Day 8, Day 15, Day 22, Day 36, Day 50 and if surgery is after week 10 (Day 64):

- Vital signs (heart rate, blood pressure and tympanic body temperature) and ECOG performance status
- Concomitant medications and adverse events will be monitored continuously
- Physical examination, haematology and serum biochemistry (Table 9-1) before treatment (Day 1) and during treatment on Day 15, Day 36, Day 50 and if surgery after week 10 (Day 64).
- TG02 treatment will be administered on Days 1, 8, 15, 22 and 36. If surgery after week 10 TG02 treatment will also be given at week 10 (Day 64).
- Pembrolizumab will be given on Days 22 and 36. If surgery is scheduled after Day 50/Week 8, pembrolizumab will be given at Day 50/Week 8. If surgery scheduled after Day 64/Week 10, a further pembrolizumab infusion will be given at Day 64/Week 10.
- DTH tests will be performed at baseline (Day 1), week 4 (Day 22), week 6 (Day 36) and week 8 (Day 50) (if surgery is scheduled for week 8 the DTH test should be performed two days before surgery). If surgery is after week 10, and the patient has had negative DTH tests up to and including week 8, an additional DTH test should be performed at week 10 (Day 64).

- Blood samples for in vitro assessment of TG02-specific immune responses (Immunology sample, PBMC) will be taken at baseline (Day 1) and Day 50. If surgery is after week 10, an additional sample should be taken as close as possible up to the date of surgery (see separate Immune monitoring plan).
- The CEA biomarker will be evaluated at Day 50. If surgery is after week 10 a third sample will be taken at Day 64 or just prior to surgery, whichever is the more appropriate.
- Tumour samples for assessment of immune response will be taken at time of surgery. If for any reason the patient will not have surgery a biopsy will be obtained if possible at the latest by week 14 (see separate Immune monitoring plan).
- FDG PET-CT scan for tumour assessment of standard uptake value (SUV-max) as close as possible up to date of surgery.
- Circulating Tumour Cells (CTC) will be evaluated at Day 1 and Day 50. If surgery is after week 10, an additional sample can be taken as close as possible up to the date of surgery.

Additional monitoring during the first 2 hours after any TG02-treatment:

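### Protocol 8.7 lets a patient restart TG02 after a related, systemic, non-allergic toxicity of grade 3 or higher; the one line that might stop it is ambiguous

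*Protocol*

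**What the plan says.** Protocol 8.7 handles TG02/GM-CSF toxicity under two headings.

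- **General toxicity.** For related toxicity on a scheduled dosing day, "TG02 treatment should be delayed until toxicity resolved to CTC grade 1. The patient should then restart at the next planned visit". No upper grade, maximum delay or permanent stop is stated.
- **TG02- or GM-CSF-related reactions.** These bullets cover allergic signs, local reactions, and then steps split by whether the patient has had prophylaxis. The branch without prophylaxis opens with "If after the TG02 DTH dose the patient exhibits a Grade 1 or 2 allergic reaction" and continues "If a Grade 3 or 4 reaction occurs then no more vaccinations should be given". The branch with prophylaxis stops vaccination from grade 2.

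A further line, under pembrolizumab-related reactions, reads "The patient should be discontinued if immunosuppressive agents are used at immunosuppressive doses".

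Protocol 6.2 (repeated in SAP 3.2) defines unacceptable toxicity for reactions related to TG02 and/or GM-CSF. The list is introduced with "As a general rule the following will be reviewed to provide a guide to safety decisions". It includes "Other relevant clinically significant toxicity" of grade 3 or higher, apart from treatable nausea and vomiting, and it allows SSC discussion of laboratory-only findings. The stated consequence applies if more than 1 of the first 3 patients has a dose-limiting toxicity: the SSC is to "make a final decision if the rest of the patients may be enrolled".

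**The concern.** Section 6.2 says which events are unacceptable, and 8.7 tells the site what to do with the patient who had one. The two are not joined. The consequence in 6.2 concerns enrolment of other patients, while the general rule in 8.7 sends the affected patient back to dosing after recovery.

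Protocol 4.5 expects no direct benefit from the immunotherapy on surgical outcome or cure, and these patients are awaiting radical surgery. Re-dosing after an event the protocol itself calls unacceptable should need more than site judgement. The same wording governs both parts, and the practical value of a change lies in Part II, where the protocol describes the combination with pembrolizumab as novel.

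**Working it through.** The plan has no figure to reproduce: there is no formal sample size and no hypothesis (Protocol 11.1, 11.2). The check is a reading of the text, followed by a count of the doses at stake.

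**Step 1. Follow one event through the text.** Take related grade 3 fatigue. Protocol 4.2 reports one such event with the precursor vaccine TG01, in a trial that also gave gemcitabine.

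- Under 6.2, if judged clinically significant, it meets the definition of unacceptable toxicity.
- Under the general rule in 8.7, if it is present on a dosing day, treatment is delayed to grade 1 and then restarted. Grade 4 is handled the same way.
- If it peaks and resolves between visits, the general rule does not act, because it looks only at toxicity present on the dosing day.

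**Step 2. Do the stop lines reach it?** The steps begin with an allergic reaction after the DTH dose and divide patients by prophylaxis, and general toxicity has its own heading. That favours an allergic-only reading. However, the grade 3 or 4 line omits the word allergic, the heading above it covers all TG02- or GM-CSF-related reactions, and 6.2 uses the word reactions for its whole list. There are two outcomes:

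- allergic only: the fatigue event is re-dosed;
- literal: the fatigue event is stopped, and the general rule, which says restart, contradicts it.

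Either way 8.7 needs correction. For injection-site reactions of grade 3 or higher, the reach of the line is likewise unclear.

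**Step 3. Does another section supply the stop?**

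| Provision | What it does | Grade-based stop or required approval? |
|---|---|---|
| 7.5, adverse events | Withdrawal if the investigator and/or patient wants it or thinks it necessary | No, discretionary |
| 7.5 with exclusion 5h (adverse reactions to peptide vaccines) | Withdrawal if the investigator and/or sponsor considers it necessary | No, discretionary |
| 9.2.1.2, serious events | Report within 24 hours; call within 2 hours if life-threatening or fatal | No; a severe event need not be serious |
| 6.2 and 13.5, SSC | Reviews the first three patients in each part; general oversight later | No per-patient rule stated |
| 8.7, immunosuppressive doses | Discontinuation | No, depends on the treatment given |
| SAP 5.1 | Summarises delays and discontinuations | No |

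**Step 4. Count the doses at stake.** Protocol 6.4.2 states "TG02 treatment will be administered on Days 1, 8, 15, 22 and 36", plus Day 64 if surgery is after week 10. DTH injections are on Days 1, 22, 36 and 50, plus Day 64 if surgery is after week 10 and earlier tests were negative. The number remaining is the count of scheduled days after the dose in question.

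| Event after dose (day) | Treatments left (with Day 64) | DTH injections left (with Day 64) |
|---|---|---|
| 1 (Day 1) | 4 (5) | 3 (4) |
| 2 (Day 8) | 3 (4) | 3 (4) |
| 3 (Day 15) | 2 (3) | 3 (4) |
| 4 (Day 22) | 1 (2) | 2 (3) |
| 5 (Day 36) | 0 (1) | 1 (2) |

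Pembrolizumab starts on Day 22. After that day the TG02 injections left are 1 + 2 = 3, or 2 + 3 = 5 with Day 64. These are upper bounds that assume recovery to grade 1 by the next visit. If one scheduled treatment is missed for recovery, the treatments left become 3, 2, 1, 0, 0 (4, 3, 2, 1, 0 with Day 64).

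**The case against.** The strongest reply is that the stop may already be there. The grade 3 or 4 line is not limited to allergy by its own words. A reader might infer from the general rule that 8.7 plainly lacks any stop for these events. The text does not support so flat a claim, because the line's reach is ambiguous. This stands, and it changes the diagnosis: the defect is either a missing rule or two conflicting ones.

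A reader might also infer that a site acts alone when it re-doses. That too goes beyond the documents. Life-threatening events, and those requiring hospitalisation, are serious and are reported quickly; the SSC reviews the first three patients in each part; and 7.5 gives the sponsor a possible route to withdrawal. The SSC charter, not available here, may hold an individual rule. All of this stands as mitigation, but none of it is written as an approval needed before the next dose.

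Two further replies have some weight. The documents describe low expected toxicity: peptides generally lack inherent toxicity (4.7), and no related serious event was reported in the first four TG02 patients (4.2). After pembrolizumab starts, at most two TG02-treatments remain. The largest counts above therefore belong to events before any pembrolizumab.

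Finally, the proposed rule still permits resumption, so in many cases the change amounts to one SSC contact. That is an accurate description of a modest fix. It does not show that the present wording is adequate.

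**Conclusion.** The point holds as a defect in the dosing rule and should be corrected, with medium confidence. On the natural reading, a related, systemic, non-allergic event of grade 3 or higher leads to restart after recovery to grade 1. On the literal reading, 8.7 contradicts itself for the same event. The existing safeguards are partial.

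At most 5 TG02-treatments remain after a first-dose event, and at most 2 after a Day 22 event. Both figures assume surgery after week 10 and prompt recovery. They count exposure and do not measure risk: the documents give no event rate, so no probability of harm follows. The conclusion also rests on the charter containing no individual rule. If it does contain one, 8.7 should still state it or refer to it, since that is where sites are told how to manage toxicity.

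**What to change.** Change 8.7 as follows.

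1. Keep both existing stop lines absolute, and state that the grade 3 or 4 line covers allergic and injection-site reactions.
2. Limit delay-and-restart to events below the 6.2 threshold.
3. Add: a patient with any other TG02- or GM-CSF-related toxicity that meets the 6.2 definition, judged on the worst grade since the last dose, receives no further TG02 or GM-CSF, including DTH injections, unless the SSC agrees to resumption after recovery to grade 1. The patient stays on study for surgery, samples and safety follow-up.

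Using the 6.2 definition keeps its exclusion of treatable nausea and vomiting and its SSC discussion of laboratory-only findings. Pembrolizumab remains under the existing instruction to follow its product information.

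The cost is three or four sentences and one SSC contact per event. Affected patients may also receive fewer doses and DTH tests: at most 5 treatments and 4 DTH injections fewer after a first-dose event, and 2 and 3 fewer after a Day 22 event. DTH response is part of a primary immune endpoint and Part II enrols at most 10 patients, so this loss is real. Patients who reach surgery stay in the efficacy set, with fewer doses.

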8.8. Prior and Concomitant Medications

No systemic anti-cancer therapy is to be used during the study treatment period before surgery.

Other vaccinations must not be administered during the treatment period.

Vaccination with yellow fever or live (attenuated) vaccines is prohibited until after surgery.

Any agent with a known effect on the immune system should be excluded during the treatment period before surgery, unless it is being given at dose levels that are not

immunosuppressive, e.g. prednisone at 10 mg/day or less or as inhaled steroid at doses used for the treatment of asthma.

No specific studies of interactions between TG02 and other agents have been conducted.

9. STUDY ASSESSMENTS

9.1. Assessment of Efficacy

9.1.1. Primary Efficacy Variables

A systemic immune response is defined as having a positive in vivo DTH and/or a positive in vitro T-cell response at least once during the treatment period. Change intra-tumoural T-cells in resected tumour tissue at surgery compared to pre TG02-treatment core biopsy will be investigated.

Delayed Type Hypersensitivity (DTH)

DTH tests are performed in order to demonstrate whether a TG02 RAS mutation specific immune response has been elicited.

[figure not shown]
Administration of TG02 only (without GM-CSF or preceded by TG02-treatment) must be injected intradermally in the lower area of the contralateral arm to TG02-treatment as a Delayed Type Hypersensitivity (DTH) test.

The DTH test is administered at baseline (Day 1 before treatment) week 4, week 6 and week 10 if surgery is scheduled after week 10 and the patient has not shown positive DTH reaction.

The DTH skin reaction assessment is to be performed 48 hours (+/- 4 hours) after each administration by the patient in a study specific diary. The patient will be instructed by the study nurse how to record the DTH response and how to enter the results into the diary. The DTH-test will be considered positive if the area of the skin reaction has an average diameter* of ≥ 5 mm at the 48 hours (+/- 4 hours) assessment ([Figure 4](#)).

Figure 4: DTH Skin Reaction Registration (induration and erythema)

* Average diameter: $\frac{a \text{ mm} + b \text{ mm}}{2}$

T-cell Analyses

Immunology-processed blood samples (PBMC) will be taken at baseline (Day 1, Week 1) and week 8 (Day 50). If surgery is after week 10, a third sample will be taken as close as possible up to the date of surgery. All samples will be processed and stored under appropriate conditions until being analysed in batches to minimize day to day assay variability. PBMCs will be analysed for the presence of TG02 specific T-cells which will be described in a study specific Immune Monitoring Plan.

Tumour biopsy assessment

Tumour samples for assessment of immune response will be taken pre TG02-treatment (baseline) in the form of a study specific biopsy as per site specific standard protocol (optimally 2 cores will be needed) and at time of surgery in the form of resected tumour tissue (post treatment sample). If for any reason the patient does not proceed to surgery, a biopsy will be obtained at the time of planned surgery if possible. In addition, archival biopsy samples from both initial staging (primary diagnosis) and re staging will be utilised, as needed.

The tissue samples should be fixed in 10% neutral buffered formalin as soon as practical after collection of the specimen. Processing of tumour tissue into blocks will occur according to the respective sites standard histology sampling procedure. These tumour tissue samples will be used for pathological review and subsequent immunohistochemically evaluation of potential biomarkers.

In addition, from some patients, fresh tumour tissue will be sent directly to the laboratory at Peter MacCallum Cancer Centre following the respective sites standard procedures. These fresh tissue samples will be processed to isolate tumour infiltrating cells (TILs) and to generate tumour-derived organoid/spheroid cultures as part of other outcome measures.

As for the primary efficacy variables, tumour infiltrating lymphocytes in resected tumour tissue at surgery and baseline biopsies will be analysed by immunohistochemistry.

The collection, storage, shipment, parameters and analyses to be used will be described in the study specific Immune Monitoring Plan.

